#### 3.4.2 *Biopsy & Fiducial Marker Placement*

- See Appendix III for MRI- Guided biopsy and FM data form
- Post fiducial marker placement MRI's may be performed to evaluate for marker migration

#### 3.4.3 *Radiation Treatment Phase*

- Weekly AP (or PA) and lateral port films
- The following acute rectal toxicity endpoints will be measured.
  - RTOG acute toxicity grading- GI & GU (Appendix IIA) weekly and at completion of therapy

#### 3.4.4 *Post Active Treatment Evaluation (follow- up)*

- Upon completion therapy, patients will be evaluated at 2, 4, 8, and 12 weeks for acute effects of radiation therapy. Patients will be evaluated at 6, 9, 12, 18 and every 6 months afterward for late effects until 36 months.
- Follow-up visits will include:
  - A directed history and physical examination,
  - PSA evaluation
  - Rectal toxicity assessment including:

- RTOG acute toxicity grading- GI & GU(Appendix IIA)
- RTOG Late toxicity grading- GI & GU (Appendix IIB)
- EPIC (Appendix IIIC)
- AUA Symptom Score (Appendix IV)
- Sexual Health Inventory for Men (SHIM) ( Appendix V)

- Follow-up MRI may be obtained after completion of therapy to better delineate the time of course of signal change after radiation therapy.
- Patients may volunteer for additional imaging and tissue acquisition procedures if deemed desirable by the PI or study chairperson.

### **3.5 CONCURRENT THERAPIES**

This study allows imaging and tissue procurement in localized prostate cancer patients without metastasis. Usually, such patients do not receive hormonal or chemotherapy. Some patients do receive hormone therapy prior to being seen by a radiation oncologist. Such patients will remain eligible for this study. However, it is preferred that they discontinue hormone therapy while receiving radiation.

### **3.6 SURGICAL GUIDELINES**

None other than those required for standard biopsy procedures. Where clinically indicated, biopsies will be performed under appropriate analgesia, local/systemic anesthesia and/or conscious sedation with patient monitoring in compliance with hospital standards, no general anesthesia will be administered for research purposes only. Only biopsies that are “minimal risk” and do not require general anesthesia will be performed for research purposes only. Please refer to section 3.2.2. for details on the biopsy procedures.

### **3.7 RADIATION THERAPY GUIDELINES**

Radiation Therapy is part of the primary protocol treatment and is therefore included in section 3.2.3

### **3.8 OFF STUDY CRITERIA**

**3.8.1** Patients may be taken off study for the following non-medical or administrative reasons:

- Patient refuses the procedure or further treatment
- It is deemed in the patient’s best interest as determined by the PI.
- Serious protocol violation as determined by the PI.

3.8.2 *Development of a concurrent serious medical condition that precludes the completion of fiducial marker placement, radiation therapy or follow-up.*

3.8.3 *Tumor progression (if occurs during treatment, at the end of radiation therapy unless the completion of local therapy is not indicated)*

3.8.4 *Initiation of cytotoxic chemotherapy (if occurs during treatment, at the end of radiation therapy unless the completion of local therapy is not indicated)*

3.8.5 *Development of a concurrent serious medical condition during active treatment and not attributable to therapy that precludes the completion of active treatment.*

3.8.6 *The completion of 36 months (3 years) follow-up.*

### 3.9 POST-STUDY EVALUATION

- At the time a patient comes off study the reason for withdrawal should be documented.
- The patient should be registered off- protocol by completing the Off Study/Death Notification Form available from the web site (<http://home.ccr.cancer.gov/intra/eligibility/welcome.htm>) and faxing it to the Central Registrar's Office at [contact].

### 4.0 SUPPORTIVE CARE

These procedures may require supportive care including nursing care, local anesthetic, analgesics, anti-emetics, and antibiotic prophylaxis. Please refer to section 3.2.2.2 – 3.2.2.3 for details. In the event that a patient has a reaction (allergic) to the contrast agent or medications, all appropriate medical measures will be taken.

The most common acute side effects of radiation therapy for prostate cancer, urethritis, cystitis and proctitis, may be treated with medications consistent with the standard of practice in the radiation oncology community. It is anticipated that a minority of patients may require short-term in-patient care for problems related to this protocol, namely an inability to void immediately post-op. In such circumstances, patients will be admitted to the Clinical Center under the care of the Urologic Oncologist. Medications should be listed in the patient's records.

### 5.0 DATA COLLECTION AND EVALUATION

#### 5.1 Data Collection

- Clinical data and acquired samples/images will be recorded in a NCI CCR database.
- Clinical data collection will include: demographic information, pathologic diagnosis, clinical stage, PSA values, history including concurrent therapies, time of biopsy, locations of biopsies, pathology reports of biopsies, dose of radiation delivered, and toxicity assessment.
- Tissue experiments to be performed are pilot and preliminary in nature. Data from assays run at the NIH will be collected in laboratory notebooks, and the NCI online microarray database.
- MRSI and dynamic MRI measurement along with corresponding sites of tissue acquisition will be digitally archived and processed using computer software in the Radiology department of the Clinical Center, NIH, and the Radiation Oncology Branch, NCI.

## 5.2 Response Criteria

Response of tumor will be determined by tracking serum PSA levels. Three consecutive rises of the PSA post-treatment will define disease recurrence. The time of disease recurrence will be back-dated to the first rise in PSA. This methodology is as prescribed by the American Society of Therapeutic Radiation Oncology (ASTRO.)

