## 5.4 Statistical Section

This is a phase I study to determine the maximum tolerated dose (MTD) with MRI-guided radiation dose escalation to regions of interest within the prostate gland. The dose cohorts and MTD are defined in Section 3.1.1. With this design, the probabilities of dose escalation are 0.91, 0.49, 0.17, and 0.03 if the probability of a DLT is 0.1, 0.3, 0.5, and 0.7, respectively.

Secondary analyses include (i) evaluating the frequency of late term toxicities, and (iii) correlating radiation response and /or toxicity with genomic and proteomic analyses. We will tabulate the frequency of late term toxicities. We will analyze differences in gene expression between responders and non-responders as well as between patients with toxicity and without toxicity by conducting, on a gene by gene basis, two-sample t-tests at the 0.001 level. We will also conduct permutation tests to test for overall differences in gene expression between these patient groupings. All secondary analyses will be reported as exploratory.

The total number of patients accrued to this trial will be 18 to 36 patients. We anticipate accruing these patients within 2 years.

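### The PSA response rule in 5.2 has no provision for hormone therapy, so a man whose PSA is suppressed by it can be grouped as recurrence-free in the exploratory gene-expression comparison

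*Combined protocol and SAP*

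**What the plan says.** All references are to the combined protocol and SAP.

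- **5.2 Response Criteria.** PSA is the only basis for response: "Response of tumor will be determined by tracking serum PSA levels". The event is "Three consecutive rises of the PSA post-treatment will define disease recurrence", and its date is set as follows: "The time of disease recurrence will be back-dated to the first rise in PSA". There is no clause on hormone therapy, salvage treatment or censoring.
- **3.5 Concurrent Therapies.** Hormone use is described as uncommon: "Usually, such patients do not receive hormonal or chemotherapy". Of men who have already received it, the section says "Such patients will remain eligible for this study", and then "However, it is preferred that they discontinue hormone therapy while receiving radiation". That is a preference, so continuing through radiation is allowed. The period after radiation is not mentioned.
- **2.1.1.5.** The bar on prior treatment covers surgery, radiation and chemotherapy, but not hormones.
- **3.8 Off Study Criteria.** The only systemic treatment listed is in 3.8.4: "Initiation of cytotoxic chemotherapy". Item 3.8.3 lists tumor progression without defining it.
- **5.1.** The history of concurrent therapies is collected.
- **5.4 Statistical Section.** The classification is used here: "We will analyze differences in gene expression between responders and non-responders", gene by gene, with two-sample t-tests at the 0.001 level. Secondary analyses are labelled exploratory. No rule uses the therapy history.

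**The concern.** Hormone therapy lowers PSA whether or not the radiation controlled the tumor. A rule that recognises failure only through successive PSA rises therefore cannot see a failure while hormones hold PSA down. There are two routes:

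1. A man stays on hormones from before or during radiation, and his PSA says little about the radiation.
2. A man has one or two rises, starts hormones because of them, and does not produce the third.

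The second route is not random error. Treatment is given because the PSA is rising, so the men moved out of the recurrence group are likely to be true failures. The comparison serving objective 1.1.2.1 would then set a depleted non-responder group against a responder group that contains some failures.

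**Working it through.** **Plan's own figures.** No figure is stated for the PSA analysis. The only calculated figures in 5.4 are the escalation probabilities. With DLT probability p, the formula is (1−p)³ + 3p(1−p)²·(1−p)³. For p = 0.1, 0.3, 0.5 and 0.7 it gives 0.906, 0.494, 0.172 and 0.032, against the stated 0.91, 0.49, 0.17 and 0.03. They reproduce and contain no PSA term, so nothing here bears on the MTD.

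**Applying the rule literally**

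| Situation after radiation | Three rises observed? | Label under 5.2 |
|---|---|---|
| Hormones start after the third rise | Yes | Recurrence; no harm done |
| Hormones start after one or two rises, PSA suppressed | Not while suppressed | No recurrence |
| Hormones continued from before or during radiation | Not while suppressed | No recurrence |
| PSA rises despite hormones, or after they stop | Possible | Recurrence, true or false |

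The gap is in the second and third rows.

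**How long is the exposed period?** Section 3.4.4 sets visits at 6, 9, 12 and 18 months, then every 6 months to 36, with PSA at each. Counting rises first seen at month 6 or later:

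- at 6, 9 and 12 months: 12 − 6 = 6 months from first to third;
- at 9, 12 and 18 months: 18 − 9 = 9 months;
- at 12, 18 and 24 months, or any later series: 12 months (for example 30 − 18).

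Hormones started within that span can prevent the third rise if they act before the next draw. A start just before the third draw need not.

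**How many recurrences might there be?** Section 1.2.2 cites 3-year PSA relapse-free rates of 92%, 86% and 81% by risk group after whole-gland IMRT, matching the 36-month follow-up. Recurrence is then 8% to 19%. The planned total is 18 to 36; 30 is an assumed middle case.

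| Men | Recurrences at 8% | Recurrences at 19% | One masked man, as share of recurrences |
|---|---|---|---|
| 18 | 18 × 0.08 = 1.4 | 18 × 0.19 = 3.4 | 69% to 29% |
| 30 | 30 × 0.08 = 2.4 | 30 × 0.19 = 5.7 | 42% to 18% |
| 36 | 36 × 0.08 = 2.9 | 36 × 0.19 = 6.8 | 35% to 15% |

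For 30 men, two masked would be 2/2.4 = 83% to 2/5.7 = 35%.

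**Effect on the responder group.** With 30 men and 5.7 recurrences, two masked men give 30 − 5.7 + 2 = 26.3 apparent responders, of whom 2/26.3 = 7.6% are failures. With 2.4 recurrences and one masked, the share is 1/28.6 = 3.5%. So contamination of the responders is modest. The main damage is the loss of men from a non-responder group that is very small to begin with.

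**The case against.** The case on the other side has several parts.

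- **The off-study criteria may catch these men.** A man with rising PSA might leave under 3.8.3 or by the investigator's judgement under 3.8.1, with the reason documented under 3.9. A reader might infer from 5.2 that he stays on study to 36 months; the documents do not say that. But leaving the study does not make him a non-responder, so the label stays open.
- **Responder is never defined.** This stands. Grouping men without three rises as responders is an inference, though 5.2 supplies no other PSA criterion.
- **Suppression is not permanent.** A reader might infer that such men can never meet the rule. They can, if PSA rises despite hormones or after they stop.
- **Hormone use is said to be unusual.** The sentence in 3.5 describes localized patients in general; the section then acknowledges that some do receive it, and it does not address salvage use. The number affected may still be small.
- **The rule is attributed to a professional society's standard.** Whether that standard covers treatment begun before a third rise cannot be checked here. The gap is shown only for this document.
- **The analysis is exploratory.** Correct, and this limits the importance of the point. A reader might also infer that the PSA control of the escalated dose would look too good, but neither the objectives nor 5.4 plan such an estimate.

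**Conclusion.** The point holds in a limited form. Applied as written, 5.2 can leave a man whose PSA is suppressed by hormones labelled recurrence-free, and no other section corrects the label. The consequence is confined to the exploratory responder versus non-responder comparison; the MTD, the DLT rules and the sample size are unaffected.

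The size cannot be fixed, because the documents give no rate of hormone use. With 30 men and recurrence of 8% to 19%, there would be about 2 to 6 non-responders, and one masked man would be 18% to 42% of them. This assumes that rates from a cited whole-gland series, with a median follow-up of 24 months, carry over to this trial. That one or two men would be masked is a supposition, not an estimate. A reader might infer that a fixed fraction of failures, such as a third, would be lost; nothing in the documents supports a particular fraction.

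**What to change.** In 5.2:

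1. Define a non-responder as a man with three consecutive PSA rises, or who starts hormone or other salvage therapy for rising PSA after radiation. In both cases, date the event to the first rise.
2. State that a man is not assessable for PSA response while he remains on hormone therapy continued from before or during radiation.
3. Apply both rules using the concurrent-therapy history collected under 5.1, checking that it records start and stop dates and the reason for starting.

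Censoring or stratification would also be workable; what matters is that one rule is stated before the groups are formed. This is an analysis rule only. It takes no position on whether hormone therapy should be given.

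The cost is a short addition to 5.2, with no added visits or patients. A few men become not assessable, and a man treated early for a rise that would not have persisted would count as a non-responder.

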## 5.3 Toxicity Criteria

- Acute toxicities will be evaluated by the CTC, Version 3.0. (<http://ctep.info.nih.gov>).
- We will also utilize the RTOG acute and Late toxicity GI/ GU scales as in appendices II A & B

## 5.4 Statistical Section

This is a phase I study to determine the maximum tolerated dose (MTD) with MRI-guided radiation dose escalation to regions of interest within the prostate gland. The dose cohorts and MTD are defined in Section 3.1.1. With this design, the probabilities of dose escalation are 0.91, 0.49, 0.17, and 0.03 if the probability of a DLT is 0.1, 0.3, 0.5, and 0.7, respectively.

Secondary analyses include (i) evaluating the frequency of late term toxicities, and (iii) correlating radiation response and /or toxicity with genomic and proteomic analyses. We will tabulate the frequency of late term toxicities. We will analyze differences in gene expression between responders and non-responders as well as between patients with toxicity and without toxicity by conducting, on a gene by gene basis, two-sample t-tests at the 0.001 level. We will also conduct permutation tests to test for overall differences in gene expression between these patient groupings. All secondary analyses will be reported as exploratory.

The total number of patients accrued to this trial will be 18 to 36 patients. We anticipate accruing these patients within 2 years.

### **5.5 Data Safety and Monitoring Plan**

#### *5.5.1 Plan for monitoring the progress of the trial and the safety of participants*

- PI will assume primary responsibility for monitoring the progress of the trial and the safety of participants.
- As part of the NCI CCR, this trial may be selected at random to be monitored by the staff of Harris Technical, Inc.
- Data will also be submitted to the NCI IRB annually for continuing review and at the completion of the study.
- In addition, at monthly research/ protocol meetings, senior staff of the NCI ROB will review protocol progress and provide feedback to the PI.

#### *5.5.2 Plan for assuring the compliance with the requirements for reporting adverse events*

- Adverse events will be reported as in section 5.3 and 7.3

#### *5.5.3 Plan for assuring that any action resulting in suspension of the trial is reported to the IRB*

This is an intramural NCI CCR protocol without external sponsors. If the NCI IRB issued the suspension, it would necessarily be aware. If another group issued a suspension of the trial, the PI would assume responsibility for notifying the NCI IRB.

#### *5.5.4 Plan for assuring data accuracy and protocol compliance*

- Data will be collected as in section 5.1
- Clinical data will be recorded in either the 4th Dimension Database or in the NCI CCR database or both.
- Data integrity and protocol adherence are assured by regular data verification and protocol compliance checks performed by the research team (PI, research nurse, data manager and clinic nurse).

## **6.0 HUMAN SUBJECTS PROTECTIONS**

### **6.1 RATIONALE FOR SUBJECT SELECTION**

This is a study for patients with prostate cancer. The patient population in whom this disease occurs is older adult males. This disease does not occur in children; therefore, children will not be part of this study. All ethnic groups/ race categories would be represented as they are represented in the disease as a whole. Decisionally impaired individuals

will not be included in this study, if they are unable to sign informed consent. Physically impaired persons who otherwise satisfy eligibility criteria will be included in this study.

## 6.2 PARTICIPATION OF CHILDREN

Adenocarcinoma of the prostate is not a disease of children, therefore, children will not be considered as research subjects for this study.

## 6.3 EVALUATION OF BENEFITS AND RISKS/DISCOMFORTS

The medical risks associated with this study are those normally expected risks associated with external beam radiotherapy for prostate cancer. Common acute and temporary side effects include fatigue, urethritis, cystitis and proctitis. Uncommon long-term side effects may include urinary frequency, urgency, incontinence, rectal bleeding, perineal pain, tenesmus, erectile dysfunction, and infertility. Very rare long-term complications may include lymphedema, pathologic femoral neck fractures, and a second primary malignancy.

Patients on this study will be receiving treatment for their prostate cancer. Other potential benefits of participation may include fewer side effects of radiation treatment due to a better visualization of the anatomy and sparing of normal structures. The information learned from this study may also benefit other patients with prostate cancer in the future.

## 6.4 CONSENT AND ASSENT PROCESSES AND DOCUMENTS

The Principal Investigator and associates will recruit patients. The investigational nature and objectives of this study, the procedures involved and their attendant risks and discomforts, will be carefully explained to the patient, and a signed informed consent document will be obtained. It is our goal to be as explicit as possible in verbal and written consent procedures to insure that all participants are joining the study without coercion.

Patients who meet study eligibility criteria, and who are willing to participate in the study, will be consented by the PI or associate investigators. The consent form will be discussed with the patient in person. Informed consent will involve careful explanation of all items outlined in the consent form. This discussion includes the investigational nature of this study, and the possibility of lack of direct benefit to the research subject. All information will be reported in summary fashion only. A separate anesthetic/operative consent will be obtained at the time of the procedure

## 6.5 PATIENT ADVOCATE

The patient's rights representative is available to patients on this protocol at [contact] in [name], NIH. Patients may ask any questions about the study and may withdraw their consent at any time without compromising their medical care.

## **7.0 DATA REPORTING**

### **7.1 PATIENT REGISTRATION FORM**

Demographic information and results of pretreatment studies should be entered and reported to Harris Technical, Inc., at the time of patient entry onto the trial (see section 2.3).

### **7.2 DATA SUBMISSION**

- Summary information will be submitted to the IRB annually for continuing review and at the completion of the study.
- Data may be reported in laboratory publications as derived from pilot studies. Patients will not be indicated by name.
- The number of MR-identified abnormalities in the initial evaluation that are biopsied and whether or not they are confirmed pathologically as cancer will be reported in the annual continuing review application to NCI IRB.

### **7.3 Definitions**

#### **7.3.1 Adverse Events**

An adverse event is defined as any reaction, side effect, or untoward event that occurs during the course of the clinical trial associated with the use of a drug in humans, whether or not the event is considered related to the treatment or clinically significant. For this study, AEs will include events reported by the patient, as well as clinically significant abnormal findings on physical examination or laboratory evaluation. A new illness, symptom, sign or clinically significant laboratory abnormality or worsening of a pre-existing condition or abnormality is considered an AE. All AEs must be recorded on the AE case report form unless otherwise noted above in Section 5.1.

All AEs, including clinically significant abnormal findings on laboratory evaluations, regardless of severity, will be followed until satisfactory resolution. AEs should be reported up to 30 days following the last dose of study drug.

An abnormal laboratory value will be considered an AE if the laboratory abnormality is characterized by any of the following:

- Results in discontinuation from the study
- Is associated with clinical signs or symptoms

- Requires treatment or any other therapeutic intervention
- Is associated with death or another serious adverse event, including hospitalization.
- Is judged by the Investigator to be of significant clinical impact
- If any abnormal laboratory result is considered clinically significant, the investigator will provide details about the action taken with respect to the test drug and about the patient's outcome.

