### 7.4.2 NCI-IRB Requirements for PI Reporting at Continuing Review

*For reporting of adverse events at time of continuing review, the NCI-IRB requires a summary report of adverse events that have occurred on the protocol **since the previous continuing review and in aggregate**. The method of presentation should provide the NCI-IRB with the information necessary to clearly identify risks to participants and to make a risk: benefit determination. Please sort the events by the system organ class and by grade. The summary report is based on the following guidance: any unexpected severity and/or unexpected frequency of expected events needs to be reported and interpreted in relation to the risk: benefit of study participants in the narrative.*

*Please use following table for reporting adverse events at time of CR:*

System Organ Class	CTCAE Term	Grade	# of Events since last CR	Total # of Events	Attribution to Research	Serious?	Unexpected?

The protocol PI will report to the NCI-IRB:

1. A summary of all protocol deviations in a tabular format to include the date the deviation occurred, a brief description of the deviation and any corrective action.
2. A summary of any instances of non-compliance
3. A tabular summary of the following adverse events:

- All Grade 2 **unexpected** events that are possibly, probably or definitely related to the research;
- All Grade 3 and 4 events that are possibly, probably or definitely related to the research;
- All Grade 5 events regardless of attribution;
- All Serious Events regardless of attribution.

**NOTE:** Grade 1 events are not required to be reported.

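### Does the 30-day limit on adverse event reporting, tied to an undefined study drug, leave late events unreported?

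*Combined protocol and SAP*

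**What the plan says.** The limit stands in section 7.3.1, among the definitions: "AEs should be reported up to 30 days following the last dose of study drug". The same section sets the recording rule: "All AEs must be recorded on the AE case report form unless otherwise noted above in Section 5.1". Section 5.1 contains no such exception; its list of data to be collected ends with "dose of radiation delivered, and toxicity assessment". Section 7.3.1 also has every adverse event followed until it resolves.

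The intervention is radiation. Section 3.7 states that "Radiation Therapy is part of the primary protocol treatment". The only drugs described, in section 8, are an antibiotic, a local anesthetic, an MRI contrast agent and an enema, and none of them is called the study drug.

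On routes of reporting, section 5.5.2 says "Adverse events will be reported as in section 5.3 and 7.3" and does not mention 7.4. Section 7.4.2 asks at each continuing review for "a summary report of adverse events that have occurred on the protocol", covering the period since the last review and the cumulative total. Its list includes "All Grade 3 and 4 events that are possibly, probably or definitely related to the research" and "All Serious Events regardless of attribution", as well as related unexpected grade 2 events and all grade 5 events. It sets no cut-off after treatment.

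**The concern.** A reporting window needs a start, and this one is tied to something the trial does not have. Staff could count from the last fraction or, read literally, from the last dose of one of the section 8 agents, and the two give very different limits. Even the more generous reading stops early in a follow-up that runs to 36 months.

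The events at stake are new ones outside the GI and GU systems that begin after day 30. Section 6.3 names lymphedema, femoral neck fracture and second malignancy as long-term risks, and these would be expected mainly after the window had closed. If the 30-day sentence overrode 7.4.2, the IRB could weigh risk against benefit on an incomplete record. No passage says in so many words that the 7.4.2 classes are exempt from the limit.

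**Working it through.** The plan gives no figure of its own on this point, so there is none to reproduce. The check is a count of visits, followed by a side-by-side reading.

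**Visits (section 3.4.4), in days from the end of radiation**
- Weeks 2, 4, 8, 12 × 7 = days 14, 28, 56, 84.
- Months 6, 9, 12, 18, 24, 30, 36 × 30.44 = about days 183, 274, 365, 548, 731, 913, 1,096.
- Total: 4 + 7 = 11 visits.

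**Reading A: the clock starts at the last fraction**
- Inside 30 days: days 14 and 28, so 2 visits. Outside: 11 − 2 = 9, and 9/11 = 82%.
- Share of follow-up time: 30/1,096 = 2.7%.
- Any limit from 28 to 55 days gives the same 2 and 9.

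**Reading B: the clock starts at the agents given for the biopsy (an assumption)**
- Radiation begins once pathology is available (section 3.2.3.2, Radiation Treatment) and lasts at least 7 weeks (3.1.3): 7 × 7 = 49 days.
- The window would close at least 49 − 30 = 19 days before radiation ended, with all 11 visits outside.
- This sits badly with weekly toxicity grading through treatment (3.4.3). Contrast may also be given again at a follow-up MRI. Reading A is the one that staff would sensibly adopt.

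**What depends on the 30-day sentence under Reading A**

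| Use of the data | Governing text | Bound by 30 days? |
|---|---|---|
| DLT and escalation | 3.1.3, 3.1.4: RTOG acute GI/GU grade, 12 weeks or 3 months after radiation | No |
| Late GI/GU toxicity | 3.4.4, 5.3: RTOG late grading at visits to 36 months | No |
| Recording on the case report form | 7.3.1, with 5.1 stating no exception | No |
| Events already open at day 30 | 7.3.1: followed to resolution | No |
| Deaths (other than from progression) and Unanticipated Problems | 7.4.1: within 7 working days | No limit stated |
| Listed event classes at continuing review | 7.4.2, sorted by organ class; on study until 36 months (3.8.6) | No limit stated |
| Other new events after day 30 | 7.3.1 | Yes |

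Only the last row is cut off. It holds new events that are non-serious, below grade 5, and either unrelated to the research or of low grade (grade 1, or grade 2 and expected). Section 7.4.2 does not ask for these at any time.

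**The named late risks.** A fracture or second malignancy would be looked for at visits that include a history and physical examination (3.4.4). If serious, it falls under 7.4.2 whatever its cause; if related and grade 3 or 4, it falls there too. Section 7.3.10 counts an event as unexpected by nature, severity or frequency. Section 6.3 ranks these risks as very rare, while one case in this trial would be 1/36 = 2.8% to 1/18 = 5.6% of patients. A single case could therefore be unexpected in frequency and go to the IRB under 7.4.1 as well, provided the other two conditions of 7.3.10 are met.

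**The case for a change.** The strongest case for acting is that the 30-day sentence is the only adverse event window in the document and its reference point does not exist. The section meant to assure compliance with reporting, 5.5.2, leads the reader to that sentence and not to 7.4. The secondary objective on long-term effects (1.1.2.2) and the tabulation planned in 5.4 are not confined to GI and GU events. Yet the late scale covers only those systems, and 5.3 names a CTC version for acute toxicities only. Rewording would cost almost nothing.

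The wording defect stands, and so does the incomplete cross-reference. The claimed loss of information does not. Section 7.4.2 is a specific requirement of the IRB and binds without being cited in 5.5.2; 5.5.1 and 7.2 also commit to annual submission. A general sentence among the definitions is not naturally read as cancelling it, and the two can apply together. The main remedy on offer, reporting the 7.4.2 classes through 36 months, repeats what 7.4.2 already asks. Re-anchoring the sentence to the last fraction would leave the same 9 visits outside the general window. The CTC version for late events outside GI and GU is a separate, small point: the 7.4.2 table already calls for a CTCAE term and grade.

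**Conclusion.** No change to the plan follows. Section 7.3.1 carries drug-trial wording into a radiation trial, and 5.5.2 omits 7.4. Both are clerical, and a team running the trial would read them sensibly. The count of 9 visits out of 11 is correct from the last fraction, but that anchor is assumed, and examination and RTOG grading continue at all of those visits. The documents give no basis for estimating how many events, if any, would go unreported.

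This rests on two readings: that the continuing-review duty in 7.4.2 covers events for as long as a patient is on study, and that the recording rule in 7.3.1 is not itself cut at 30 days. Both follow from the text as it stands. The sponsor may tidy the term and the cross-reference if the document is amended for another reason, but no endpoint, escalation decision or conclusion depends on it.
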